The primary outcome for the calculation of the sample size was defined as the effect of the cTBS protocol and the iTBS protocol (both in combination with cognitive training) compared to the treatment involving the combination of cognitive training with TBS placebo and the one which involves only the TBS protocol applied in isolation, on the MMSE score obtained at the end of the treatment. Based on the results of a previous rTMS study on a sample of AD patients (Ahmed et al., 2012), we estimate that at the end of our treatment there will be an improvement in the MMSE score of at least 3 points (SD of change = 2.95) for protocols that involve the combination of cognitive training and real TBS, and of 0.2 points (SD of change = 2.7) for the treatment that involves the combination of cognitive training and placebo TBS.

Considering an alpha value of 0.05 and a power of 0.80, we estimate that the number of patients to be recruited should be 16 patients per group, increased to 20 per group to take into account a possible dropout rate of 20%.

Techniques provided for data processing

Behavioral and neurophysiological data will be analyzed by analysis of variance (ANOVA) and post-hoc comparisons (t-test, contrast analysis).

Statistical processing software

Data processing will be performed with BrainVision Analyzer, SPSS and/or Statistica software.

ETHICAL CONSIDERATIONS AND ASSESSMENT OF THE RISK/BENEFIT RATIO

Expected benefits

Based on the assumptions of the present project, patients who will receive the treatment that involves the combined application of rTMS and cognitive training should show a clinical response, based on the primary endpoints reported above, better than the patients assigned to the protocols in which rTMS and cognitive training are applied in isolation. The research also provides indirect scientific/cognitive benefits, in terms of advancing knowledge on the development of treatments with proven efficacy and on the mechanisms underlying Alzheimer's dementia.

Potential Risks

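### The MMSE comparison that sets the sample size appears in the analysis only as a post-hoc test after an ANOVA, so the stated 0.80 power is not the power of the analysis named

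*Protocol*

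**What the plan says.** Under Calculation of sample size, the protocol defines the sizing outcome as the effect of each combined protocol (cTBS or iTBS with cognitive training) on MMSE at the end of treatment. The comparators are cognitive training with placebo TBS "and the one which involves only the TBS protocol applied in isolation". The inputs are "an improvement in the MMSE score of at least 3 points (SD of change = 2.95") for the combined protocols and "of 0.2 points (SD of change = 2.7) for the treatment that involves the combination of cognitive training and placebo TBS". The result follows: "Considering an alpha value of 0.05 and a power of 0.80, we estimate that the number of patients to be recruited should be 16 patients" in each group, raised to 20 for dropout.

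Under Techniques provided for data processing, a few lines later, the whole method is that "Behavioral and neurophysiological data will be analyzed by analysis of variance (ANOVA) and post-hoc comparisons (t-test, contrast analysis").

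The opening of the Statistical Analysis section lists the factors: time (t0 to t4), type of treatment protocol (three levels: combined, TBS alone, training alone), type of stimulation, and clinical group. It gives example comparisons but does not say which test answers the primary objective.

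**The concern.** The sample size calculation treats one pairwise comparison as the test that decides the trial. The analysis text puts that comparison among the post-hoc tests. Post-hoc is the usual word for tests read after a significant overall F, and the protocol does not declare the sized comparison a planned contrast.

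Two readings are open. If the pairwise test waits for the F, success needs both tests to be significant. The power of that procedure can only be equal to or lower than that of the pairwise test. If it does not wait, the overall or interaction F and the pairwise test can each be presented as the result, and the 0.80 belongs to only one of them. Which test decides should be fixed before the data are seen.

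**Working it through.** **Inputs from the protocol.** Mean gain 3 (SD of change 2.95) in the combined arms; 0.2 (SD 2.7) in training plus placebo TBS; "Considering an alpha value of 0.05 and a power of 0.80"; "16 patients per group, increased to 20 per group to take into account a possible dropout rate of 20"%. There are five arms, with 20 AD and 20 MCI patients in each (Study Design), so a sized group is one diagnosis within one arm.

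**Assumptions.** No gain is given for TBS alone, so it is varied from 0.2 to 3.0 with SD 2.95. Sidedness is not stated.

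**Step 1: reproduce the stated size.** With the two-sided normal formula,

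n = (1.960 + 0.842)² × (2.95² + 2.7²) / (3 − 0.2)² = 7.85 × 15.99 / 7.84 ≈ 16.01 per group.

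A one-sided 0.05 gives (1.645 + 0.842)² × 15.99 / 7.84 = 12.6, that is 13, so the stated 16 matches a two-sided test. Dropout: 16 / (1 − 0.20) = 20. The figure is therefore a plain two-group comparison at full alpha, with no overall F in it.

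**Step 2: power of that comparison alone.** At 16 per group the normal formula gives 0.80 and the exact t-test gives 0.77. This 3-point gap comes from the normal approximation and has nothing to do with an ANOVA.

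**Step 3: power if a five-arm F must be significant first.** Simulated end-of-treatment change, 16 per arm, mean gains (3, 3, x, x, 0.2), where x is the TBS-alone gain. The pairwise test is one combined arm against training plus placebo. Simulation error is about 0.01.

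| x | t-test alone | F and t both significant | t significant, F not | F significant, t not |
|---|---|---|---|---|
| 0.2 | 0.77 | 0.75 | 0.02 | 0.17 |
| 1.0 | 0.77 | 0.69 | 0.08 | 0.10 |
| 1.6 | 0.77 | 0.64 | 0.13 | 0.07 |
| 2.2 | 0.77 | 0.63 | 0.14 | 0.06 |
| 3.0 | 0.77 | 0.69 | 0.09 | 0.10 |

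The gate itself costs from about 2 points (x = 0.2) to about 14 points (x = 2.2).

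**Step 4: other readings of the protocol, same range of x.**

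- Three-level treatment factor, then a single combined arm against training plus placebo: 0.71 to 0.77.
- Three-level treatment factor, then both combined arms pooled against training plus placebo: 0.79 to 0.88.
- AD and MCI pooled (32 per arm), equal effects, five-arm F then the single-arm t-test: about 0.95 to 0.97.
- The same, with each MCI arm's advantage over training plus placebo halved: about 0.70 to 0.81, against about 0.83 without the gate.

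**The case against.** **The gate is not in the document.** This is correct. The protocol never makes the post-hoc tests conditional on F; that is a convention the reader brings. A statistical analysis plan, not shown here, might also settle the order. What stands is narrower: the protocol states a power for one test and an analysis in which that test is a follow-up, and these two statements do not match as written.

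**The comparison is named in advance.** The sample size section fixes the arms, measure and time point, and the analysis text allows contrast analysis. This is fair, and it suggests what was intended. But the same sentence classes contrast analysis as post-hoc, so the intention is not carried into the analysis.

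**The five-arm F is not the factor listed.** Also fair. The listed treatment factor has three levels, and with it the loss shrinks or disappears. Clinical group is a factor too, so both diagnoses may enter one model, and with equal effects the loss then has no practical weight. The protocol does not choose among these analyses, and its sizing inputs come from a sample of AD patients only.

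**Stronger readings.** A reader might infer that power simply drops below 0.80 because of the ANOVA. The documents do not support this: the t-test alone is already at 0.77, and some readings of the factors and population stay above 0.80 even with a gate. A reader might also take power near 0.45, or two tests disagreeing in a third of trials, as the size of the problem. Those values need an arm-by-time interaction gate, a TBS-alone gain midway between the two stated gains, an effect that fades after treatment and an assumed correlation over visits. The protocol gives none of these.

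**Conclusion.** The mismatch is real and lies between two neighbouring paragraphs of the protocol. The 16 per group reproduces as an ungated pairwise test, and the analysis lists that test as post-hoc, so the 0.80 does not describe an ANOVA-then-post-hoc procedure.

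The direction is certain if a gate applies; the size is conditional. At the sized 16 per arm in one diagnosis, a five-arm gate gives about 0.63 to 0.75 against 0.77 ungated, depending on a TBS-alone gain that the protocol does not state. Collapsing to three levels makes the loss smaller. Pooling the diagnoses removes it in practice only if MCI patients benefit about as much as AD patients. That two tests in an ANOVA framework can differ is ordinary; the defect is that the protocol does not say which one decides. This is worth correcting and does not invalidate the design.

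**What to change.** State in the statistical section that the sized comparisons are planned contrasts: combined TBS with training against training plus placebo TBS, and against TBS alone, on MMSE change at end of treatment. They should be estimated in a named population (AD, MCI or both) and tested whatever the overall or interaction F shows. Give a rule for multiplicity across them, and label all other pairs and visits exploratory. If an overall gate is preferred, keep it and restate the power for the gated procedure under stated assumptions, including one for TBS alone.

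The cost is a short edit and no new data. There are two consequences. A significant overall F alone could no longer be presented as the primary result. The multiplicity rule may also affect the size: splitting alpha equally over two contrasts, for example, gives (2.241 + 0.842)² × 15.99 / 7.84 = 19.4, so 20 evaluable per group in place of 16. A fixed testing order would leave the first contrast at full alpha.
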